11.5 Sample Size Determination

The assumptions made to permit sample size determination are:

- 1) The population reference value of the proportion of patients achieving (and then sustaining) $PSA \leq 4$ ng/ml (4 or less) within 7 months of starting therapy is 50% for men on the standard (i.e., control arm, or Arm B) therapy of LHRH agonist + bicalutamide;
- 2) The hypothesized rate of patients achieving (and then sustaining) $PSA \leq 4.0$ within 7 months of starting therapy on the experimental arm (i.e., enzalutamide, or Arm A) is 75%;
- 3) significance level of 0.10, one-sided (in view of the directional hypothesis);
- 4) power = 0.80;
- 5) balanced (i.e., 1:1) randomization.

11.5.1 Under those assumptions, the required sample size is N=41 response-evaluable (r-e) patients (defined in Section 8.10) on each arm. That calculation used the method of Fleiss et al [42], and was performed with the nQuery Advisor software, Version 7.0. The total sample size required is 82 patients. Allowing for up to 10% of patients who might not become r-e, up to 46 patients per arm (a total of 92 patients) may need to be enrolled.

11.5.2 Enrollment to this study is expected to be approximately 25-30% AA (from all participating institutions). For better generalization of our study results, we seek a minimum accrual of 25 (approximately 30%) evaluable AA patients. To achieve that goal, it may become necessary to close accrual to non-AA patients at some point during the study. Let p = the primary endpoint (the proportion of patients achieving $PSA \leq 4.0$ within 7 months). With 25 AA patients, p can be estimated to within 0.183 of its true value with 95% confidence, regardless of the level of p .

11.6 Analysis

11.6.1 For the primary objective, the binary endpoint (PSA remission at month 7, yes/no) will be summarized with its point estimate (an occurrence rate), and 2-sided Wilson type 95% confidence interval (CI). This analysis will be performed two ways: a) for all randomized patients (the intention to treat subset); and b) for all r-e patients (the per protocol subset). PSA response rates will be compared by treatment arm in a stratified logistic regression model, with stratification by race (AA, Other) and bone pain (yes, no).

11.6.2 All binary endpoints in secondary objectives 1-2 and 4-7, will be summarized with point estimates (occurrence rates), and 2-sided Wilson type 95% CIs. The analysis of toxicity rates will be performed using only the toxicity-evaluable (t-e) patients (defined in Section 8.11).

11.6.3 For secondary objective 4, the grade of each type of toxicity (an ordinal categorical variable) will be summarized with 1-way frequency distributions. A similar descriptive analysis will be performed for any correlatives in secondary objective 7 to be assayed by IHC, resulting in ordinal categorical variables (intensity levels of 0, 1+, 2+, or 3+).

Dichotomized versions (e.g., the occurrence rate of Grade 3-4 neutropenia) will be summarized as described in Section 11.6.2. A similar descriptive analysis will be performed for the presence/absence of any correlatives in secondary objective 7 to be assayed by IHC, with presence defined as intensity level of 1+ through 3+.

For any correlatives in secondary objective 7 that are assayed in both pre- and post-treatment prostate tumor tissues, the change in IHC expression level will be described using a 2-way frequency distribution. If the effective sample size appears to be sufficient relative to the size of the 2-way table, the association of these paired variables can be tested with the exact version of McNemar's test.

11.6.4 All censored time-to-event distributions for secondary objectives 3 and 5 will be estimated with standard Kaplan-Meier (K-M) methodology. Point and CI estimates of the median and various time point-specific rates will be derived from the K-M life table. The censored K-M distributions will be compared with the log-rank test, stratified by race (AA, Other) and bone pain (yes, no).

11.6.5 All (uncensored) continuous variables from secondary objective 7 (e.g., ERG or CXCR4 or AR splice variant level measured by QPCR in frozen tissue, or length of CAG repeats) will be summarized with descriptive statistics including the point estimate of the mean, its associated 95% CI (or 90% CI, depending on N), median, IQR, standard deviation, minimum, and maximum. Gene expression levels reported in terms of the number of fold increases will be log₂-transformed before summary statistics are calculated.

If such variables are pseudo-continuous (e.g., 10-15 unique values), they will also be analyzed as categorical variables using 1-way frequency distributions, as described in Section 11.6.3. Pre- and post-treatment CTC counts (required to determine CTC response for secondary objective 6), will be similarly analyzed as continuous variables. Depending on their distribution, CTC counts will also be analyzed as categorical variables in the manner described in Section 11.6.5 for length of CAG repeats.

11.6.6 The association of correlative markers (whether binary, or ordinal categorical, or continuous) with a binary clinical outcome (e.g., the primary endpoint of achievement of PSA remission at month 7, yes/no) will be explored using exact logistic regression models. Point and CI estimates of the odds ratio (OR) will be calculated, but the statistical interpretation will be limited to only the direction, magnitude, and precision of the association (i.e., the OR) as these are only exploratory analyses.

11.6.7 The association of correlative markers (whether binary, or ordinal categorical, or continuous) with a time-to-event clinical outcome (e.g., OS, PFS, TTP, or time to SRE) will be explored using Cox proportional hazards (PH) regression models. Point and CI estimates of the hazard ratio (HR) will be calculated, but the statistical interpretation will be limited to only the direction, magnitude, and precision of the association (i.e., the HR) as these are only exploratory analyses.

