4.0 ELIGIBILITY CRITERIA

4.1 Inclusion Criteria:

1. Histologically confirmed prostate adenocarcinoma with metastasis either starting or recently started on LHRH analogue therapy. [Late induction permitted within 3 months of starting LHRH analogue therapy or antiandrogen] All patients who have not initiated hormone therapy (Early induction patients) must have elevated PSA ≥ 4 ng/ml within 28 days prior to registration. For late induction registrations, PSA must be ≥ 4 ng/ml prior to start of androgen deprivation therapy; either antiandrogen or LHRH analogue or GNRH antagonist .If patients are on antiandrogen, this will need to be discontinued for at least 7 days prior to registration.
2. Patients with a history of prior neoadjuvant or adjuvant hormone therapy are eligible provided they have received twenty four or less months of hormone treatment (single or combination treatment, excluding orchiectomy). Neoadjuvant/adjuvant hormone therapy must have been discontinued at least 6 months prior to registration. This is intended to exclude patients who might have been rendered indirectly androgen insensitive.
3. There must be no plans to receive concomitant chemotherapy, biological response modifiers, radiation therapy or hormonal therapy. Concomitant radiation therapy is allowed for the palliation of severe pain/neuropathic compression.
4. Prior or concomitant use of megestrol acetate for the treatment of hot flashes is allowed.
5. Patients must have a performance status of 0 - 2 by Zubrod Criteria.
6. Patients must have recovered from any major infections and/or surgical procedures and, in the opinion of the investigator, not have significant active medical illness precluding protocol treatment or survival.
7. No prior malignancy is allowed except for adequately treated basal cell (or squamous cell) skin cancer, superficial or in situ cancer of the bladder. For an invasive cancer the patients should be disease free for at least 3 years prior to enrollment on study.
8. For all patients a bone scan must be performed within 60 days prior to registration for tumor assessment. CT scans (abdomen and pelvis) and chest x-ray are optional, but must be repeated if used for disease assessment. For late induction registrations, tumor assessment imaging showing metastatic disease must be available prior to start of androgen deprivation therapy.
9. Age 18 or older and willing and able to provide informed consent.

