---Hypotension as indicated by systolic blood pressure < 86 millimeters of mercury (mmHg) at the Screening visit;

---Bradycardia as indicated by a heart rate of < 50 beats per minute on the Screening ECG;

---Uncontrolled hypertension as indicated by systolic blood pressure > 170 mmHg or diastolic blood pressure > 105 mmHg
8. Gastrointestinal disorder affecting absorption (e.g., gastrectomy, active peptic ulcer disease within last 3 months);
9. Treatment with concurrent 5- α reductase inhibitors (finasteride, dutasteride), estrogens, and/or cyproterone
10. Treatment with systemic biologic therapy for prostate cancer (other than approved bone targeted agents and GnRH-analogue therapy) or other agents with anti-tumor activity within 4 weeks of enrollment (Day 1 visit);
11. History of prostate cancer progression on ketoconazole;
12. Prior use, or participation in a clinical trial, of an investigational agent that blocks androgen synthesis (e.g., abiraterone acetate, TAK-700, TAK-683, TAK-448) or agents that block the androgen receptor (e.g., ARN-509)
13. Previous enzalutamide therapy;
14. Use of an investigational agent within 2 weeks of enrollment (Day 1 visit);

15. Use of herbal products that may have hormonal anti-prostate cancer activity and/or are known to decrease PSA levels (e.g., saw palmetto) or systemic corticosteroids greater than the equivalent of replacement steroids or > equivalent of 10 mg of prednisone per day within 4 weeks of enrollment (Day 1 visit);
16. Any condition or reason that, in the opinion of the Investigator, interferes with the ability of the patient to participate in the trial, which places the patient at undue risk, or complicates the interpretation of safety data.
17. Prior chemotherapy for metastatic disease.
18. ≥30 days of antiandrogen therapy monotherapy without androgen deprivation therapy.
19. Life expectancy of 6 months or less.

5.0 TREATMENT PLAN:

5.1 Patient Registration and Data Collection:

All patients shall be registered with the Cancer Center Clinical Trials Office at [contact] ([name]).

At the time of registration, a pre-study form and all information required to verify eligibility shall be necessary on each patient prior to treatment. This form should be faxed to [contact] and eligibility verification will be sent within 48 hours. Data will be collected and maintained on study specific electronic case report forms in the Oncore Research Enterprise system at

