Karmanos Cancer Institute. Training and support will be provided for all staff entering data. Data entry must occur within 2 weeks of visits along with submission of applicable source documentation. The only concomitant medication data to be submitted is administration of bisphosphonate or denosumab.

5.2 Stratification and randomization procedures:

The registering data manager will first stratify the patient by race (AA or other) and cancer related bone pain at diagnosis of metastatic disease (present or absent) into one of 4 strata. Even if pain is well controlled/resolved at present the patient will be considered positive for bone pain. The patient will then be randomized to Arm A or Arm B using the stratum-appropriate randomization list prepared in advance by the study statistician [name]. Arms A and B are defined in the Study Schema (on page 5) and in Section 5.3 below. Each of the 4 randomization sequences will use random permuted blocks of varying sizes. The treatment arm randomization and enrollment confirmation will be communicated to site staff in writing within 24-48 hours from receipt of all eligibility source documents. Study treatment should start within 7 days of registration.

5.3 Study design and plan:

Overall Study Design and Plan

This study is a multicenter Phase II, randomized, screening study of oral MDV3100 (160 mg/day) in patients with metastatic hormone sensitive prostate cancer. Patients must not have received prior cytotoxic chemotherapy for metastatic disease. Radiation therapy, and initiation of

bisphosphonates or other approved bone targeting agents, and standard of care steroid and pain management are allowed and should not result in discontinuation of study drug therapy.

For patients eligible for late induction registration the treatment start date will be the date of initiation of GNRH analogue or antagonist, with or without antiandrogen. Late induction patient visits will be adjusted based on the length of their prior hormone therapy. Study drug therapy should be continued as long as the patient is tolerating the study drug and continues androgen deprivation therapy or until confirmed radiographic disease progression or a skeletal related event AND one of the two following events: 1) initiation of another agent for treatment of prostate cancer. Or 2) Intolerance to therapy.

Patients will be randomized to receive either:

ARM A

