All lesions (or sites of disease) not identified as target lesions, including pathological lymph nodes and all non-measurable lesions, should be identified as non-target lesions and be recorded at baseline. Measurements of these lesions are not required and they should be followed as 'present', 'absent' or in rare cases, 'unequivocal progression'.

Evaluation of target lesions

Complete Response (CR): Disappearance of all target lesions. Any pathological lymph nodes (whether target or non-target) must have reduction in short axis to <10 mm.

Partial Response (PR): At least a 30% decrease in the sum of diameters of target lesions, taking as reference the baseline sum of diameters.

Progressive Disease (PD): At least a 20% increase in the sum of diameters of target lesions, taking as reference the smallest sum on study (this may include the baseline sum). The sum must also demonstrate an absolute increase of at least 5 mm.

Stable Disease (SD): Neither sufficient shrinkage to qualify for PR nor sufficient increase to qualify for PD.

Confirmation

In non-randomized trials where response is the primary endpoint, confirmation of PR and CR is required to ensure responses identified are not the result of measurement error. This will also permit appropriate interpretation of results in the context of historical data where response has traditionally required confirmation in such trials. However, in all other circumstances, (i.e., in randomized phase II or III trials or studies where stable disease or progression are the primary endpoints), confirmation of response is not required since it will not add value to the interpretation of trial results. However, elimination of the requirement for response confirmation may increase the importance of central review to protect against bias, in particular in studies which are not blinded. In the case of SD, measurements must have met the

SD criteria at least once after study entry at a minimum interval (in general not less than 6–8 weeks) that is defined in the study protocol.

8.1 Primary Endpoint:

The proportion of patients on either arm achieving a PSA nadir of 4 or less (< 4 ng/ml) at month 7 of protocol therapy.

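### Cheap improvement, not a defect: the primary model in 11.6.1 leaves out the pre-ADT PSA that eligibility requires, although success is an absolute PSA cut-off

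*Combined protocol and SAP*

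**What the plan says.** **Analysis (11.6.1).** Each arm's PSA remission rate is reported with a Wilson 95% interval, for all randomized and for response-evaluable patients. Rates are then "compared by treatment arm in a stratified logistic regression model, with stratification by race (AA, Other) and bone pain (yes, no". Randomization uses the same two factors (11.4.2). No section names baseline or pre-ADT PSA as a covariate or stratum, and the exploratory marker models in 11.6.6 and 11.6.7 do not list it.

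**Endpoint (8.1).** Success means "achieving a PSA nadir of 4 or less (< 4 ng/ml) at month 7 of protocol therapy". This is an absolute level and not a percentage fall.

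**Eligibility (4.1, item 1).** Patients who have not started hormone therapy "must have elevated PSA ≥ 4 ng/ml within 28 days prior to registration". For late-induction registrations, "PSA must be ≥ 4 ng/ml prior to start of androgen deprivation therapy; either antiandrogen or LHRH analogue or GNRH antagonist". Late entry is defined by "Late induction permitted within 3 months of starting LHRH analogue therapy or antiandrogen". Neither route has a PSA ceiling, and the late route has no time window for the PSA value.

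**Earlier hormone therapy (4.1, item 2).** "Neoadjuvant/adjuvant hormone therapy must have been discontinued at least 6 months prior to registration".

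**Data (5.1).** At registration, "a pre-study form and all information required to verify eligibility shall be necessary on each patient prior to treatment". The documents do not say that the pre-ADT PSA number and its date are case report form fields.

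**The concern.** With an absolute cut-off, the fall that a patient needs depends on where he starts. A patient starting ADT at 5 ng/ml needs a 20% fall; one starting at 500 ng/ml needs 99.2%. A link between pre-ADT PSA and the endpoint is therefore plausible, and eligibility has to be verified on this value in every patient.

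If PSA is prognostic, some of the sampling error in the arm comparison comes from chance imbalance in PSA between two groups of 41, and a covariate can remove that part at no cost in patients. Section 11.4.1 uses this result to decide whether to plan a larger study, so extra precision has some value. The choice has to be made before outcomes are seen, because adding PSA after an imbalance has been noticed would look selective.

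**Working it through.** **1. The plan's sample size.** Inputs from 11.5: 50% v 75%, one-sided 0.10, power 0.80, 1:1 allocation.

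- Uncorrected: n = [1.2816 × √(2 × 0.625 × 0.375) + 0.8416 × √(0.75 × 0.25 + 0.50 × 0.50)]² / 0.25² = (0.877 + 0.557)² / 0.0625 = 32.9, so 33 per arm.
- Continuity-corrected: (32.9 / 4) × [1 + √(1 + 4 / (32.9 × 0.25))]² = 40.5, so **41 per arm, as stated**.
- Allowance: 41 / 0.90 = 45.6, so 46 per arm and 92 in total, as stated.

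Without the continuity correction, approximate power at 41 per arm is 86.3%. The planned analysis therefore starts above its 0.80 target.

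**2. Fall needed to reach 4 ng/ml.** From 5: (5 − 4) / 5 = 20%. From 500: (500 − 4) / 500 = 99.2%. This makes a prognostic link plausible but does not measure it.

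**3. Simulation.** 20,000 trials per scenario, 41 per arm, marginal success rates fixed at 75% and 50%. The model has arm and four race-by-bone-pain stratum terms, without and with one log PSA term, and a one-sided Wald test at 0.10. Assumptions not in the documents: 30% African American, 40% with bone pain, no stratum effect on outcome, normally distributed log PSA, and the odds ratio (OR) of failure per SD of log PSA. The Monte Carlo SE of a power gain is 0.1 to 0.2 points.

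Mixed induction, one common slope fitted; gain in power (points):

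| Late-induction share and their OR | Early OR 2 | Early OR 3 | Early OR 4 |
|---|---|---|---|
| 75%, OR 1 | −0.2 | +0.1 | +0.1 |
| 50%, OR 1 | +0.3 | +0.8 | +1.2 |
| 25%, OR 1 | +1.0 | +2.4 | +3.1 |
| 50%, OR 1.5 | +1.4 | +2.1 | +2.8 |

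Same slope in all patients:

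| OR per SD | Planned power | With log PSA | Gain (points) |
|---|---|---|---|
| 1 | 0.867 | 0.864 | −0.3 |
| 1.5 | 0.870 | 0.876 | +0.6 |
| 2 | 0.870 | 0.891 | +2.1 |
| 3 | 0.871 | 0.914 | +4.3 |
| 4 | 0.869 | 0.929 | +6.0 |

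A separately coded simulation (6,000 trials, 50% with bone pain, common slope) gave −0.1 / +0.9 / +2.4 / +4.1 / +6.6 points at the same ORs. A repeat of the 50%-late, no-effect case gave about +0.1 / +0.7 / +1.4 at early OR 2 / 3 / 4.

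**4. Type I error.** 0.107 to 0.114 planned and 0.101 to 0.108 adjusted; 0.101 to 0.109 and 0.104 to 0.113 in the separate simulation. No difference is claimed. The slight excess over 0.10 occurs with both models.

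**5. Precision of a between-arm risk difference.** The plan does not state this measure; it is the added summary proposed below. Common slope in all patients, at OR 1.5 / 2 / 3 / 4:

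- SD unadjusted to adjusted: 0.103 to 0.102 / 0.103 to 0.099 / 0.103 to 0.094 / 0.104 to 0.091. The squared ratio (from unrounded SDs) is worth 2 / 9 / 20 / 30% more patients; at OR 3, (0.1028 / 0.0938)² = 1.20. With half late and no effect in them it is 0 / 3 / 5% at OR 2 / 3 / 4.
- A one-SD chance imbalance is √(2/41) = 0.221 SD of log PSA. Times slopes of 0.084 / 0.142 / 0.194 / 0.228, it shifts the unadjusted difference by 1.9 / 3.1 / 4.3 / 5.0 points, against a sampling SD of about 10 points.

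**6. Conditional log odds ratio.** Its SE goes from 0.49 to 0.50 / 0.51 / 0.53 / 0.58 / 0.61 at OR 1 / 1.5 / 2 / 3 / 4. In the common-slope runs power still rises at OR 1.5 and above, because the conditional estimate also moves away from zero.

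**The case against.** The strongest reply is that nothing needs repair. The model uses the randomization factors, a recognised choice. Power is near 0.87 against a target of 0.80, and 11.4.1 calls the comparison non-definitive. The benefit rests on a prognostic effect that the documents never quantify: the Background links the PSA nadir to survival, not pre-ADT PSA to reaching 4 ng/ml. All of this stands, and it is why the point is graded as an improvement.

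Late induction also weakens the case, and this stands too. The larger gains need a strong slope in most enrolled patients, so a moderate effect confined to early-induction patients may bring almost nothing.

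Three further limits apply. A PSA taken near registration is also measured before study drug, so preferring the pre-ADT value in late-induction patients is a judgement; the two were not compared. A stratified logistic model could be read as conditional logistic regression, whereas the simulation used stratum terms. The fix also adds an effect measure, so it is more than one line.

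A reader might infer that chance PSA imbalance biases the planned test. The documents do not support that: under randomization the imbalance is already part of the sampling error. A reader might also infer from 5.1 that the PSA value is already held as data for everyone. That section requires eligibility to be verifiable but does not show a data field.

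**Conclusion.** The point holds as a cheap improvement. The planned primary comparison is valid and adequately powered, and the stated 41 per arm stands.

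The gain in power from log pre-ADT PSA is about 0 to 1 point if half the patients are late-induction with no effect in them, and about 1 to 6 points if one slope with OR 1.5 to 4 holds in everyone. The loss is about 0.3 points if PSA is not prognostic. The OR and the late-induction share are assumptions, so none of these figures is a forecast. The equivalent gains of 2 to 30% more patients and the imbalance shifts of 1.9 to 5.0 points apply only to the added risk difference with a common slope. They should not be read as a shortfall in an estimate that the plan reports.

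**What to change.** In 11.6.1, before outcomes are seen:

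- Add log-transformed pre-ADT PSA as a covariate alongside the race and bone-pain strata.
- Define it as the last value before the current ADT course for metastatic disease, with the start taken as the first of antiandrogen, LHRH analogue or GnRH antagonist, as in 4.1 item 1. For early induction, use the value within 28 days before registration. Neoadjuvant or adjuvant therapy stopped under 4.1 item 2 does not count as this start.
- Do not substitute the calendar's pre-study or day-1 PSA (7.0). In late-induction patients it follows the start of ADT, and 5.3 adds that "Late induction patient visits will be adjusted based on the length of their prior hormone therapy". It can serve in a further sensitivity analysis.
- Record the PSA value and its date in the analysis data.
- State a simple missing-value rule that keeps all randomized patients in, for example the overall mean of log PSA, set without regard to arm or outcome.
- Keep the current model as a sensitivity analysis.
- Report a standardised risk difference with its confidence interval beside the conditional odds ratio, labelled as an added summary.

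The cost is a short addition to the text, two data items, one degree of freedom, a value-selection rule for late-induction patients, and a larger SE for the conditional log odds ratio. The sample size does not change.

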The results of the CHARTED (ECOG led) trial [13] were recently presented at the annual ASCO meeting in June 2014. The study randomized patients with metastatic prostate cancer to receive androgen deprivation therapy +/- docetaxel chemotherapy. The patients on the docetaxel arm received a maximum of 6 cycles of docetaxel at a dose of 75mg/m² and were started on therapy within 4 months of initiating androgen deprivation therapy. Patients were stratified based on disease volume; low volume and high volume. The latter was defined as the presence of visceral metastases and/ or 4 or more bone metastases. 64% of the patients on the hormone therapy only arm and 67% on the docetaxel arm had high volume disease. The overall survival results reveal an OS benefit with the addition of docetaxel (Hazard ratio 0.63, $p= 0.0006$) with median survival of 42.3 and 52.7 months in the hormone and chemotherapy arms respectively. A median survival improvement of 17 months was noted in the high volume disease patients. (Median survival of 32.2 months and 49.2 months). Within the low volume disease patient population the OS results have not been reported. The above results have changed the standard of care to incorporate docetaxel based chemotherapy in the management of high volume hormone sensitive metastatic prostate cancer. Based on these results and remaining cognizant of the changing standard of care we will amend the eligibility criteria of the protocol to include patients with metastatic disease who either have

a) low volume disease

or

b) patients who are not candidates for docetaxel chemotherapy

or

c) Patients refusing docetaxel chemotherapy.

Race in prostate cancer

African American (AA) men are 1.6 times more likely to be diagnosed with prostate cancer and 2.4 times more likely to die of the disease as compared to Caucasian (CA) men. The disparity is not entirely related to access to care as was shown by a study conducted in the Veterans Health system which found an OS disparity between AA and CA patients[7]. It appears that African American patients had a lower chance of maintaining the PSA nadir of 4ng/ml or less as compared to the entire group and are likely to have shorter progression free survival.[8] Even in patients treated with hormone therapy for advanced prostate cancer on clinical trials the overall survival outcome was noted to be shorter in patients of AA racial origin in both SWOG and RTOG trials.

[9,10]

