10. Willingness to swallow pills and no medical condition that would interfere with this.
11. Male patient and his female partner who is of childbearing potential must use 2 acceptable methods of birth control (one of which must include a condom as a barrier method of contraception) starting at screening and continuing throughout the study period and for 3 months after final study drug administration. Patients are also required to use a condom if having sex with a pregnant woman.
12. Patient should agree to a tumor tissue biopsy prior to protocol enrollment. Post therapy biopsy is optional.
13. Patients who are being treated with a GNRH antagonist should be willing to switch to a LHRH analogue after registration.
14. Patients must have one of the following a) Low volume disease (defined as no visceral metastases and < 4 bone metastases) or b) are not candidates for docetaxel based chemotherapy or 3) refused docetaxel chemotherapy

4.2 Patients must NOT meet any of the following exclusion criteria:

1. History of seizure or any condition that may predispose to seizure (e.g., prior cortical stroke, significant brain trauma) at any time in the past. Also, history of loss of consciousness or transient ischemic attack within 12 months of Day 1 visit;
2. Known or suspected brain metastasis or active leptomeningeal disease;
3. Severe concurrent disease, infection, or co-morbidity that, in the judgment of the Investigator, would make the patient inappropriate for enrollment;
4. Absolute neutrophil count < 1,000/ μ L, or platelet count < 50,000/ μ L, or hemoglobin < 8 /dL) at the Screening visit.
5. Total bilirubin, alanine aminotransferase (ALT) or aspartate aminotransferase (AST) > 2.5 times the upper limit of normal
6. Creatinine > 177 μ mol/L (2 mg/dL)
7. Clinically significant cardiovascular disease including:
 - Myocardial infarction within 6 months;
 - Uncontrolled angina within 3 months;
 - Congestive heart failure New York Heart Association (NYHA) class 3 or 4, or patients with history of congestive heart failure NYHA class 3 or 4 in the past, unless screening echocardiogram or multi-gated acquisition scan performed within 3 months results in a left ventricular ejection fraction that is \geq 45%;

---History of clinically significant ventricular arrhythmias (e.g., ventricular tachycardia, ventricular fibrillation, torsades de pointes);

---History of Mobitz II second degree or third degree heart block without a permanent pacemaker in place;

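### The primary model omits pre-treatment PSA although the endpoint is an absolute PSA cutoff, and disease volume is in neither the strata nor the model; the test stays valid but loses some power and protection against chance imbalance

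*Combined protocol and SAP*

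**What the plan says.** Section 11.6.1 states that response rates will be "compared by treatment arm in a stratified logistic regression model, with stratification by race (AA, Other) and bone pain (yes, no". Sections 5.2 and 11.4.2 randomise within the same four race-by-pain strata. No other baseline variable appears in the primary analysis.

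The endpoint (Study Schema, 8.1, 11.5) is a PSA of 4 ng/ml or less, an absolute level rather than a percentage fall. Inclusion criterion 1 requires a PSA of at least 4 ng/ml for everyone: within 28 days before registration for men who have not started hormone therapy, and before the start of androgen deprivation (ADT) for late-induction men.

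Criterion 14 sets three alternative routes of entry. The first is "Low volume disease (defined as no visceral metastases and < 4 bone metastases"). The others are not being a candidate for docetaxel and refusing it. Section 2.0 explains the amendment by a docetaxel trial that stratified on disease volume. In its high-volume patients that trial reported "Median survival of 32.2 months and 49.2 months" without and with docetaxel, against 42.3 months for all hormone-only patients. Section 2.0 adds that low-volume survival had not been reported. Criterion 8 makes the bone scan mandatory, but abdominal and pelvic CT and chest x-ray optional.

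**The concern.** A man who enters just above the PSA threshold has far less to achieve than one who enters with a very high value, so baseline PSA can be expected to predict remission. It is available for every patient and costs nothing to use. Leaving it out of a logistic model gives up power and lets a chance difference in starting PSA pass into the treatment comparison.

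Disease volume raises the same question more weakly. Eligibility was amended because of it, and men with low- and high-volume disease can both enter. The randomisation and the analysis were not updated to match.

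At stake is the decision in 11.4.1 on whether to plan a larger study. If the arms turn out unbalanced and no adjustment was pre-specified, any later adjustment is post hoc.

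**Working it through.** **1. The plan's own sample size.** Inputs from 11.5: "significance level of 0.10, one-sided (in view of the directional hypothesis"); power 0.80; a control rate "within 7 months of starting therapy is 50% for men on the standard (i.e., control arm, or Arm B) therapy"; a rate "on the experimental arm (i.e., enzalutamide, or Arm A) is 75"% in Arm A; "balanced (i.e., 1:1) randomization".

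- Uncorrected: n' = [1.2816·√(2·0.625·0.375) + 0.8416·√(0.25 + 0.1875)]² / 0.25² = 32.9, so 33.
- With the continuity correction: n = (n'/4)·[1 + √(1 + 4/(n'·0.25))]² = 40.5, so 41 per arm.

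This matches the plan: "The total sample size required is 82 patients". Allowing for 10% non-evaluable, 41/0.90 = 45.6, so 46 per arm and 92 enrolled. At 41 per arm, power is 0.80 with the correction and 0.86 without it. A simulated Wald test therefore starts near 0.87, not 0.80.

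**2. Baseline PSA.** The fall needed to reach 4 ng/ml is 1 − 4/PSA. This is 20% from an illustrative 5 ng/ml and 1 − 4/500 = 99.2% from 500. The chance difference between arms in mean log PSA has a standard deviation of √(2/41) = 0.22 SD.

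Simulation: 41 per arm, marginal rates 50% and 75%, one-sided 0.10, and an assumed log-odds slope per SD of log PSA.

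| Assumed slope | Change in power from adding log PSA |
|---|---|
| 0 | loss of under 0.5 points |
| 0.5 | gain of about 1 point |
| 1.0 | gain of about 4 points |
| 1.5 | gain of about 7 points |

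Type I error stayed near 0.10 with and without the covariate. A repeat run of 3,000 trials per setting agreed on power to within about a point.

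**3. Chance imbalance in disease volume.** The high-volume share in this trial is not given, so 30-65% is assumed. SD = √(2p(1−p)/41); tail probabilities are exact for two independent binomials, counting both directions.

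| High-volume share | SD (points) | ≥10 points | ≥15 points | ≥20 points | ≥15 points, 46 per arm |
|---|---|---|---|---|---|
| 30% | 10.1 | 28% | 12% | 4% | 14% |
| 50% | 11.0 | 32% | 15% | 6% | 17% |
| 65% | 10.5 | 30% | 13% | 5% | 15% |

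The shift in the observed difference is the remission gap times the imbalance. With assumed gaps of 20 and 30 points, a 15-point imbalance shifts it by 0.20 × 15 = 3 and 0.30 × 15 = 4.5 points, against a planned effect of 25.

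**4. What adjusting for volume does.** Simulation: 4,000 trials per setting, 41 per arm, high-volume shares 35-65%, 30% African American and 40% bone pain assumed, and no effect of race or pain on outcome.

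- Overall type I error: about 0.10-0.12 with or without volume.
- Power: from 0.86-0.88 to 0.87-0.89, a gain of 0.5 to 1.7 points for gaps of 20-30 points. A separate run of 3,000 trials per setting (50% share, gaps 20-40 points) gave 0.4 to 2.5.
- No gap: a change of 0.5 points or less.
- No true effect, Arm A with at least 15 points fewer high-volume men (6-8% of trials): false-positive rate 0.16-0.29 unadjusted, 0.09-0.16 adjusted.
- True effect, Arm A with at least 15 points more (50% share, gaps 20-40): power 0.70-0.78 unadjusted, 0.85-0.90 adjusted.

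The conditional rates rest on about 200-330 trials each, so they carry a Monte Carlo standard error of roughly 2-3 points.

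**The case against.** Randomisation leaves every unstratified factor to chance, the stratification factors are already in the model, and 11.4.1 calls the comparison non-definitive. Overall type I error is unaffected and power already exceeds 0.80. All of this stands. It limits the point to an improvement in the analysis.

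A reader might go further and infer that disease volume is a strong known prognostic factor, recorded at entry for every patient, whose omission undermines the primary test. The documents do not support that.

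- **Recording.** Only the first route of criterion 14 needs a volume classification. The definition needs visceral status, yet CT and chest x-ray are optional. Coding volume from the entry route would misclassify a low-volume man who entered as refusing docetaxel.
- **Prognosis.** The evidence is for survival only (32.2 months in high-volume disease against 42.3 overall on hormone therapy). No figure links volume to month-7 remission. Section 2.0 treats the PSA nadir as a surrogate for later outcome, which makes a link plausible but does not measure it.
- **Validity.** Harm from omitting volume is conditional on a sizeable imbalance. Only about half of such imbalances favour Arm A.

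Model size is a fair worry. Under the planned rates about 41 × 0.50 + 41 × 0.25 ≈ 31 non-remissions are expected. Treatment, race, pain and log PSA leave about 31/4 ≈ 8 per term; adding volume leaves about 6. This is a reason to keep volume out of the primary model. One pre-specified PSA term is affordable, and the simulation shows almost no loss if it proves uninformative.

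**Conclusion.** The point holds in a limited form. The planned test is valid. It omits a covariate tied directly to the endpoint and required at entry for every patient, at a cost of about 1 to 7 points of power for slopes of 0.5 to 1.5 per SD, and nothing if the slope is zero.

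For disease volume, the average gain is about 0.5 to 2.5 points. The main benefit is protection in the 12-15% of trials with an imbalance of at least 15 points at 41 per arm (14-17% at the 46 per arm of the intention-to-treat set). That supports a sensitivity analysis, not a change to the primary model or the strata.

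The effects of PSA and volume on remission, the volume mix and the stratum shares are all assumptions. The documents give no estimate of either effect and no volume mix for this trial.

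**What to change.** In 11.6.1, pre-specify log PSA before ADT as a covariate alongside race and bone pain, in both analysis sets, and report the unadjusted rates and their difference beside the adjusted result. Use the criterion 1 value. For late-induction men the calendar's pre-study and day 1 PSA may already be lowered by treatment.

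For disease volume, record at baseline the bone-lesion count from the mandatory bone scan, and visceral status where imaging was done, for every patient whatever the entry route. Tabulate it by arm and pre-specify a sensitivity model that adds it, stating how unknown visceral status is handled. Do not infer volume from the criterion 14 route.

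Sample size and randomisation lists stay as they are. The cost is one baseline field, one extra term in the primary model and some SAP wording. The adjusted odds ratio becomes conditional on PSA, so it will not correspond directly to the 50% and 75% rates; this is why the unadjusted rates must stay in the report.
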